# 4.4. Initial patient assessment

After trial inclusion, each patient will receive a structured systematic medical and nutritional assessment by an experienced study-team member dietician according to the case report form (CRF) including:

- Socio-demographics (e.g., age, weight and height for calculation of body-mass index [BMI])

- If feasible, basal metabolic rate (BMR) calculated using indirect calorimetry; or if calorimetry is not feasible or tolerable, the Harris-Benedict formula will be used for estimation instead
- Baseline lean body mass (estimated with body impedance analysis [BIA])
- Baseline muscle strength (hand grip strength)
- Baseline functional status (Barthel's index)
- Medical diagnoses according to the ICD10-codes and nutritional diagnoses according to the IDNT reference manual (fourth edition)

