# 4.2. Primary, secondary and safety endpoints

All patients will be assessed daily until hospital discharge and contacted after 30 and 180 days via telephone for a structured interview by blinded study nurses to assess primary and secondary endpoints.

The primary composite endpoint is combined adverse outcome within 30 days defined as

- (a) All-cause mortality
- (b) Admission to the intensive care unit from the medical ward
- (c) Unplanned hospital readmission
- (d) Major complications (defined according to previous trials) as a new occurrence (being diagnosed after inclusion into the trial) of
  - I. nosocomial infection or abscess requiring antibiotic treatment
  - II. respiratory failure with need for invasive or non-invasive ventilation (continuous positive airway pressure, CPAP)
  - III. major cardiovascular event (stroke, intracranial bleeding, cardiopulmonary arrest, myocardial infarction with and without invasive procedure) or pulmonary embolism
  - IV. acute renal failure (defined by 2x increase of baseline creatinine or new requirement of dialysis do to volume overload or electrolyte disturbance)
  - V. gastro-intestinal failure
- (e) decline in functional status of 10% or more from admission to day 30 measured by the Barthel's index (Appendix 1). This index measures performance in activities of daily living and comprises two groups of items, one related to self-care (feeding, grooming, bathing, dressing, bowel and bladder care, and toilet use), the other related to mobility (ambulation, transfers, and stair climbing). The resulting score ranges from 100 to 0 with lower scores indicating more severe disability. For the purpose of this study, a significant decrease in functional outcome will be defined as a decrease in Barthel's index by ≥10% from admission to day 30.

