# 4.3. Randomization and study procedures

If patients fulfill all inclusion criteria, with no exclusion criteria and provide informed consent, they will be randomized in a 1:1 fashion into the intervention group or the control group according to a pre-specified, computer-generated, web-based randomization scheme using the secuTrial© Software (managed and secured by the Clinical trial Unit of the University of Basel). The randomization will be stratified for the site and initial NRS (Appendix 2). In both study groups, all patients will be re-assessed daily by the nutritional specialist to re-evaluate nutritional intake and whether nutritional targets are met. If patients in the intervention group do not reach the nutritional targets (<75%), their nutritional strategy will be escalated according to the nutritional guidelines.

We will systematically collect blood samples at admission (day 0) and on inpatient days 2, 4, 6 and 8 for later batch measurement of nutritional markers and other biomarkers. If clinically indicated, there will be pre-prandial measurement of blood glucose levels 4 times daily and insulin treatment in all patients as part of usual clinical practice. There will also be regular measurement of nutritional factors in blood and possibly 24 hour urine to assess the effectiveness of nutritional therapy (see CRF for further details).

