# 5. Selection of trial subjects

# 5.1. Recruitment

Upon hospital admission, consecutive adult (age ≥18 years) medical inpatients will be screened for undernutrition risk by the house nursing and /or physician staff, using the well-validated NRS, 2002 edition, as shown in Appendix 2.

Based on this routine screening instrument, we will check daily for eligible patients using the hospital medical information system. Patients can be included in this trial within 24-48 hours of admission if they fulfill the following inclusion criteria

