# 6.2. Blinding

Patients and caregivers will not be blinded to the intervention (i.e., no placebo-controlled intervention) as this would be neither practical not feasible given the different nutritional treatment options available. However, we will have blinded outcome assessment at day 30 and day 180 in regard to primary and secondary outcomes.

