Third, there is potential for control group "contamination", i.e., if the caregiver staff feels obliged to motivate patients in the control group to increase their food consumption. A complex intervention such as nutritional therapy must be implemented at different levels and by the full care team in the hospital. While dieticians recommend individualized strategies for patients, the physician staff need to support the strategy and motivate the patient, and, most importantly, the nursing team is key in everyday application of the strategy, i.e., actively encouraging, and if needed, feeding the patient. It will thus be important to continuously educate the caregiver staff about the intention of this trial, and the potential risks of nutritional therapy which have not yet been well-studied in the population in question. We will also study caregiver characteristics (e.g., nurse—sensitive factors potentially affecting outcome, such as nursing staff work load) to detect any impact of these variables on our intervention (ancillary project).

Fourth, it is expected that not all patients in the intervention group reach their caloric and protein goals and some may refuse enteral and parenteral nutrition. However, as a pragmatic, trial we are most interested in the effects of nutritional therapy in "real life" using a state-of-the-art algorithm. Still, we will document actual nutritional intake and later study the effect of compliance on our intervention.

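### The baseline Barthel score behind primary component (e) is not protected from knowledge of the allocation, and the 10% cut-off can be read in two ways

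*Protocol*

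**What the plan says.** **Endpoint.** Section 4.2 makes functional decline component (e) of the 30-day primary composite: "a significant decrease in functional outcome will be defined as a decrease in Barthel's index by ≥10% from admission to day 30". The synopsis and section 4.2 give the cut-off only as a percentage, never in points.

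**Baseline.** Section 4.3 says that patients who qualify and consent are allocated: "they will be randomized in a 1:1 fashion into the intervention group or the control group". Section 4.4 then describes the initial assessment: "After trial inclusion, each patient will receive a structured systematic medical and nutritional assessment by an experienced study-team member dietician". One listed item is "Baseline functional status (Barthel's index)". Section 5.1 sets the window: "Patients can be included in this trial within 24-48 hours of admission".

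**Blinding.** Section 6.2 states "Patients and caregivers will not be blinded to the intervention" and adds "we will have blinded outcome assessment at day 30 and day 180". Sections 4.2 and 15 make the same promise for follow-up. None of them mentions the baseline.

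**Role of the rater's profession.** Section 15 notes: "While dieticians recommend individualized strategies for patients".

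**Analysis.** Section 8.2 compares the arms with an unadjusted chi-square test and also reports odds ratios adjusted for baseline Barthel, centre and NRS category.

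**The concern.** A change score has two ends, and blinding one of them protects only that end. Section 15 answers the open-label objection by pointing to blinded assessment at day 30. For component (e), a rater who knew the arm could move the event count just as well by scoring the baseline one step higher or lower.

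The baseline is taken by a member of the profession that plans the intervention, at a moment described only as after inclusion. No rule requires it to precede the allocation or to come from a rater unaware of it. A systematically lower baseline in one arm would remove events from that arm, and a higher one would add them. The covariate adjustment in section 8.2 cannot correct this, because the covariate is the same measurement. The chi-square test does not use it at all.

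A second, smaller matter is that the cut-off is not fixed. On a scale from 0 to 100, a 10% fall can mean 10 points or a tenth of the patient's own starting value.

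**Working it through.** **1. The plan's own sample size (section 8.3).** Inputs: 40% versus 34%, two-sided alpha 0.05, power 0.90.

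n = [z(0.975)·√(2·p̄(1−p̄)) + z(0.90)·√(p₁(1−p₁)+p₂(1−p₂))]² / (p₁−p₂)²

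With p̄ = 0.37: [1.960·√0.4662 + 1.2816·√0.4644]² / 0.06² = 1358.6, so 1359 per group. This agrees with the protocol and is not affected by the point made here.

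**2. One step of baseline scoring can decide event status.** The item scores in Appendix 1 are all multiples of 5, so the total moves in 5-point steps. A day-30 score of 90 is an event against a baseline of 100 (fall of 10 points, 10%). It is not an event against a baseline of 95 (fall of 5 points, 5.3%). This holds under either reading of the cut-off.

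**3. Illustration of size.** From section 8.3: 10% functional decline and a 6-point target effect. Assumed, because the protocol gives neither: a normally distributed change with SD 12 to 20, and a baseline scored on average s = 2.5 points lower in one arm, for example one step too low in half of its patients. The threshold is set so that 10% decline without the shift, giving

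P(decline) = Φ(−1.2816 − s/SD)

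| SD | s/SD | P(decline) | Reduction |
|---|---|---|---|
| 12 | 0.208 | 6.8% | 3.2 points |
| 15 | 0.167 | 7.4% | 2.6 points |
| 20 | 0.125 | 8.0% | 2.0 points |

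These are changes in component (e) alone. Patients who also have another component remain events, so the composite moves by less.

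**4. What a shift in the composite would do.** Assumed shifts, 1359 per group, starting from 40%:

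| Shift | Two-sided rejection rate if there is no true effect | Power if the shift works against a true 6-point effect |
|---|---|---|
| none | 5% | 90.0% |
| 0.5 points | 5.8% | 84.3% |
| 1 point | 8.3% | 76.8% |
| 2 points | 18.8% | 57.5% |

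For the middle column, with p₂ = 0.40 − d, the rate is the normal-approximation probability that the observed difference exceeds 1.96 pooled standard errors in either direction. The last column is the power for 40% versus 34% + d.

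**5. The two readings of the cut-off on the 5-point grid.**

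| Baseline | Smallest qualifying fall, 10% of baseline | Smallest qualifying fall, 10 points |
|---|---|---|
| 0 | none possible | none possible |
| 5 | 5 points | none possible |
| 10 to 50 | 5 points | 10 points |
| 55 to 100 | 10 points | 10 points |

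Check at the boundary: 10% of 50 is 5 points, one step; 10% of 55 is 5.5 points, so two steps are needed. The readings agree from 55 upwards and differ on a 5-point fall from 5 to 50.

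**The case against.** **The order of events is not stated.** A reader might infer that the dietician scores the baseline after randomisation and knows the arm. The protocol says neither. Section 5.1 speaks of inclusion for patients who meet the criteria, which could mean enrolment before allocation. That 4.3 precedes 4.4 proves little, because the sections are not chronological: the endpoints come before randomisation, and eligibility comes after the initial assessment. The flow figure was not legible in the text reviewed and might show the order. Section 4.2 itself names the admission value, and 8.2 lists admission as the first time point. All this stands. It limits the point to a missing safeguard, and does not remove it: elsewhere inclusion serves as time zero (new complications in 4.2, costs in 13.2), and the legible text does not place the baseline before allocation.

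**The size is assumed.** A reader might take the 2.6 points at SD 15 as an estimate of bias to set against the 6-point effect. It is not. The shift and the SD are assumptions, no direction is supported, overlap is ignored, and a structured form with concrete item anchors limits drift in scoring. This stands too.

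**The cut-off does not bias the comparison.** A reader might infer that a relative cut-off favours one arm because it counts one step at low baselines and two at high ones. It does not: the same rule applies to both arms, and randomisation balances true baselines in expectation. Nor does the protocol call the cut-off relative. A 10-point rule would not cure the floor either, since it makes decline impossible at a baseline of 5 as well as at 0. What remains is the ambiguity.

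**Conclusion.** The point holds as an unprotected baseline, and bias is not demonstrated. In an open trial, the reference value for a primary-endpoint component may, as the text stands, be scored by someone who knows the allocation; neither day-30 blinding nor baseline adjustment would repair that. The component is expected in 10% of patients, so even modest differential scoring could matter beside a 6-point effect, but the actual size and direction cannot be derived from the protocol. The reduction to 6.8–8.0% depends wholly on the assumed 2.5-point shift and SD of 12 to 20.

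The cut-off is a secondary point. Its wording allows two event definitions that differ for 5-point falls from baselines 5 to 50. That needs settling because it defines part of the primary endpoint, but it is a matter of definition and not a source of bias between arms.

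The change is worth making because it is cheap. The sample size stands.

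**What to change.** - **Sections 4.3 and 4.4:** require the baseline Barthel to be entered in the eCRF before the web-based system releases the allocation. Do the same for grip strength and lean body mass where feasible; they are not primary components and need not hold up allocation.
- **Sections 4.2 and 4.4:** reconcile admission with after trial inclusion, so that one dated measurement is named as the reference for component (e).
- **Section 4.2:** state whether the cut-off is 10 points on the 0–100 scale or 10% of the patient's baseline. Analyse the other reading as a sensitivity analysis, and note the baselines at which no decline can be recorded (0 under the percentage reading, 0 and 5 under the points reading).

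Cost: one step is reordered within the existing 24–48 hour window, so a few consented patients may be assessed but not randomised; one clause is added to 4.2. If sites already score the baseline before allocation, one clarifying sentence settles the main part.

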# 5. Selection of trial subjects

# 5.1. Recruitment

Upon hospital admission, consecutive adult (age ≥18 years) medical inpatients will be screened for undernutrition risk by the house nursing and /or physician staff, using the well-validated NRS, 2002 edition, as shown in Appendix 2.

Based on this routine screening instrument, we will check daily for eligible patients using the hospital medical information system. Patients can be included in this trial within 24-48 hours of admission if they fulfill the following inclusion criteria

#### 5.2. Inclusion criteria

Included will be all consecutive medical inpatients if they meet the following criteria

- a) NRS ≥3 points
- b) expected hospital LOS ≥5 days (as estimated by the treating physician team)
- c) willingness to provide informed consent (see informed consent statement)

[figure not shown]
#### 5.3. Exclusion criteria

Excluded will be patients if they meet the following criteria

- a) initially admitted to critical care units (except intermediate care)
- b) scheduled for surgery or in an immediate post-operative state
- c) unable to ingest oral nutrition and thus need for enteral or parenteral nutrition
- d) admitted with, or scheduled for, total parenteral nutrition or tube feeding
- e) currently under nutritional therapy (defined by at least one visit with a dietician in the last month)
- f) who are hospitalized because of anorexia nervosa
- g) in terminal condition (end of life situation)
- h) hospitalized due to acute pancreatitis
- i) hospitalized due to acute liver failure
- j) earlier inclusion into this trial

- k) Cystic fibrosis
- I) Patients after gastric bypass operations
- m) Stem cell transplantation
- n) Any contraindication against nutritional therapy (i.e., enteral and/or parenteral)

Figure 2: Study flow sheet

# Outcome assessment for primary and secondary endpoints at discharge, and blinded at days 30 and 180 by study nurses:

Assessment of primary and secondary endpoints by team members by chart review and telephone Interviews (functional outcomes, mortality, disposition, QoL)

Nutritional reguirements / goals Caloric targets **Protein targets** Micronutrients Other targets Basal metabolic rate Use of 1.2g protein multi-vitamin (indirect calorimetry Fat-reduced nutrition. per Kg bodyweight / supplement, specific amino-acids, or Harris Benedict day; other supplements formula) electrolyte lower amounts in after blood analysis in & daily activity (& substitution selected patients renal failure illness factors) supplement Kcal/d g protein/d other Individualized nutritional measures to reach targets e.g., maltodextrin, rapeseed oil, cream, protein powder, in-Step 1 Food fortification between snacks, soft drinks and other products e.g., Resource Protein, Resource Compact, Fresubine Step 2 Protein Energy, Ensure Plus, Enlive Plus Drink, Fresubin plus ONS 5kcal Shot, Calshake, Nepro, and other products e.g., Peptamen AF, (Nepro), Isosource Protein Fibre, Step 3 (Nutrision), Novasource GI forte, (Impact Glutamine), plus enteral Fresubin Hepa and other products e.g., Smofkabiven, Smofkabiven EF, Structokabiven peri, Step 4 plus parenteral and other products Re-assessment every 24-48 hours: did the patient meet nutritional targets (>75%)? **Continuation of** Yes No nutritional therapy Therapy escalation

Figure 1: Nutritional strategy in the intervention group

#### 6. Assessment of effectiveness

Efficacy and response to treatment are evaluated by statistical analysis, comparing the intervention group to the control group regarding primary and secondary endpoints (see statistical analysis).

The analysis will be performed together with the clinical trial unit (CTU) of the University of Basel by using the collected data from the study database which will be similar for all participating study centers.

#### 6.1. Intervention

For the purpose of this study, we have developed nutritional guidelines by consensus and adapted to current guidelines (e.g., ESPEN, ASPEN)  (*figure 1 and Appendix 4*). Guidelines specify a reinforced nutritional therapy strategy to cover nutritional requirements, focusing on nutritional targets based on the specific nutritional diagnoses defined by the IDNT. The nutritional guidelines may vary according to important medical diagnoses (i.e. renal failure). They specify not only nutritional targets, but also escalation of the route (i.e. food fortification, oral, enteral, parenteral) if targets cannot be achieved (≤75%) every 24-48 hours.

Nutritional goals will be assessed daily in patients in the intervention group (*Figure 2*). In control patients, we will use conventional nutrition according to the ability and desire of the patient to eat, using standard care food provided by the hospital kitchen ("appetite-guided").

Nutritional therapy may be started in control patients at any time, if new swallowing disorders develop or if patients need to be prepared for surgical interventions. Similarly, nutritional therapy may be stopped in case patients in the intervention group become terminal or develop a condition where nutritional therapy is contraindicated (e.g., intestinal perforation). Thus, in both groups the nutritional therapy protocol may be overruled after discussion with the PI and the involved study coordinators.

# 6.2. Blinding

Patients and caregivers will not be blinded to the intervention (i.e., no placebo-controlled intervention) as this would be neither practical not feasible given the different nutritional treatment options available. However, we will have blinded outcome assessment at day 30 and day 180 in regard to primary and secondary outcomes.

# 7. Assessment of Safety

# 7.1. Risks of the study

We consider the risks of this study to be minimal, for the following reasons:

- Blood Loss: 7.5ml of EDTA-plasma and 7.5ml of serum as well as one additional tube (7.5ml) for determination of genetic markers will be additionally drawn on admission. All other blood draws are part of clinical routine
- Whether or not nutritional therapy has a benefit in acutely ill medical inpatients remains unclear.
   Different smaller trials have not been able to demonstrate large improvements in patient outcomes in regard to mortality and/or morbidity.
- Risks of nutritional therapy include refeeding syndrome and risk associated with enteral and
  parenteral nutrition. We will do a careful monitoring for refeeding including daily clinical visits
  and routine blood work for electrolyte dysbalance. In case of refeeding syndrome, we will lower
  the amount of nutritional therapy (50%) and also treat with B-complex vitamins. We expect that
  only a minority of patients will receive enteral and parenteral nutrition (around 10%) and in these
  patients benefits may outweigh risks.

# 8. Statistics

# 8.1. Analysis population

The primary analysis population is the full analysis set, which, following intention-to treat (ITT) principles, includes all randomized patients. Every effort will be made to minimize the number of patients lost to follow-up.

# 8.2. Statistical approach

Detailed methodology for summaries and statistical analyses of the data collected in this study will be documented in a statistical analysis plan. The statistical analysis plan will be finalized before database closure.

Briefly, a consort diagram will be reported including all screened patients, patients lost to follow up and patients included in the final analyses. Primary and secondary endpoints will be compared between trial arms in the overall ITT population and within predefined subgroups as discussed below. All outcomes will be analyzed in an uncorrected manner as well as jointly corrected for the main risk factors (Barthel's index at baseline, study center and initial NRS categories). For our primary analysis, we will compare the two arms with a chi-square test and we will also estimate effect size with a logistic regression model reporting unadjusted and adjusted odds ratios (OR) and corresponding 95% confidence intervals (CIs).

We will do different predefined subgroup analyses by including interaction terms in the regression models to test for effect modification by important baseline factors. Specifically, we will look at patients age (<60, 60-75, >75 years), gender, risk for undernutrition stratified according to initial NRS (3, 4, >4 points), BMI (<20, 20-25, >25-30, >30), main medical diagnosis (systemic infection, heart failure, acute renal failure, gastro-intestinal disease, tumor), comorbidities (diabetes, chronic renal failure).

For the analysis of functional outcome (defined by Barthel's index) we will use a non-parametric Wilcoxon rank sum test to compare Barthel's index at day 30 between randomization arms. However, to adjust for additional variables, we will also fit a multivariate linear model including Barthel's index at baseline, study center and initial NRS to estimate effect size and 95% confidence intervals (95%Cls). If needed, data will be transformed as appropriate (e.g., log transformation). Moreover, we will assess the progression of Barthel's index over time (i.e. admission, day 8, day 30) using a linear mixed model approach to account for the repeated measurements per patient.

A similar approach will be used for all other secondary endpoints where we will use chi-square tests / logistic regression analysis for binary outcomes, Wilcoxon rank sum test / linear models for continuous outcomes and log-rank test / cox regression for time-to-event data as appropriate.

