#### Secondary endpoints will be defined as follows:

- (a) each single component of the primary endpoint at day 30
- (b) each single component of the primary endpoint and the combined endpoint at short term, ie, at day 10 or hospital discharge whatever comes first
- (c) each single component of the primary endpoint and the combined endpoint at long term term, ie, at day 180
- (d) short-term nutritional and functional outcomes from inclusion to day 10 or hospital discharge (whatever comes first) including nutritional intake, improvement in muscle strength measured with handgrip strength, lean body mass, changes in undernutrition markers (pre-albumin, retinol-binding protein, body weight, BMI)];

- (e) hospital outcomes measured at hospital discharge defined as total hospital LOS, discharge home vs. post-acute care facility, new decubital ulcer;
- (f) Improvement in quality of life measured on admission and at 30-day and 180-day using the EuroQol Group 5-Dimension Self-Report Questionnaire (Appendix 3) and selected items from the Functional Assessment Anorexia-Cancer Therapy [FAACT] questionnaire),

Safety endpoints including side effects from nutritional therapy will be assessed daily until hospital discharge. A causal relationship with the trial will be rated by two study team members as unrelated / unlikely / possible / probable / definitely / not assessable. The following side effects were defined:

- a) Adverse gastrointestinal effects (diarrhea, nausea, vomiting, abdominal pain)
- b) Complications due to tube feeding or center catheter for parenteral nutrition,
- c) Refeeding syndrome,
- d) Liver or gall bladder dysfunction
- e) Hyperglycemia (defined as glucose levels >12mmol/l or persistent levels >10mmol/l in patients without diabetes or well controlled diabetes)

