# 13.2. Cost-effectiveness analysis of nutritional therapy

**Purpose:** to perform a cost-effectiveness calculation for early nutritional therapy in medical inpatients at risk for undernutrition including cost-effectiveness and cost-utility analyses. These analyses will be from the health-care payers' perspective using intervention data generated in the RCT.

**General approach:** The total cost calculation will include nutritional costs (including nutritional products and estimated time of dieticians spent with patients) and all medical costs within 30 days after study inclusion. The total cost calculation also will include all hospitalisations after index hospitalisation. We

will derive estimates of the real costs using REKOLE a comprehensive accounting algorithm used by Swiss hospitals to internally compute provider costs. Cost-effectiveness will be expressed as the incremental cost-effectiveness ratio. Non-parametric bootstrapping will be used to estimate 95%Cls for differences in incremental costs and effects. We will further calculate the probability value that nutritional therapy is cost-effective for a range of different willingness to pay values. We will define confidence intervals for the relevant cost difference. We will assume equivalence if the difference in total direct costs will lie between the equivalence margins. Non-inferiority of costs will be demonstrated if the upper limit of the confidence interval for cost differences between the two strategies will be smaller than the cost difference. In a second step we will perform a joint analysis of effects and costs in a cost-utility analysis by analysing the cost per quality adjusted life years (QALY) gained. We will present an overall analysis, and different subgroup analyses as defined in the RCT. Specifically, we will look at patients age (<60, 60-75, >75 years), gender, risk for undernutrition stratified according to initial NRS (3, 4, >4 points), main medical diagnosis (systemic infection, heart failure, acute renal failure, gastro-intestinal disease, tumor), comorbidities (diabetes, chronic renal failure), LOS (<8 days, ≥8 days) and BMI (<20, 20-25, >25-30, >30).

**Presentation of results:** To assess the shape of the joint sampling distribution of costs and effects we will present the joint density distribution of incremental costs and effects on the cost-effectiveness plane.

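### Section 8.2 names one covariate list for all outcomes, so continuous secondary endpoints other than Barthel are, read literally, not adjusted for their own collected baseline

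*Protocol*

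**What the plan says.** Protocol section 8.2 sets two analyses for every outcome, one unadjusted and one "jointly corrected for the main risk factors (Barthel's index at baseline, study center and initial NRS categories". For Barthel's index at day 30 it adds a Wilcoxon test and says "we will also fit a multivariate linear model including Barthel's index at baseline, study center and initial NRS to estimate effect size". For the rest it continues: "A similar approach will be used for all other secondary endpoints where we will use chi-square tests / logistic regression analysis for binary outcomes", with Wilcoxon tests and linear models for continuous outcomes. No further covariate is named. The section leaves detail to a separate document: "Detailed methodology for summaries and statistical analyses of the data collected in this study will be documented in a statistical analysis plan".

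The baselines exist. Section 4.4 lists "Baseline muscle strength (hand grip strength" among the initial assessments, together with lean body mass by impedance analysis and weight and height for BMI. In section 4.2 the quality-of-life endpoint reads "Improvement in quality of life measured on admission and at 30-day and 180-day", using EuroQol and selected FAACT items. The same section words handgrip as an improvement and body weight and BMI as changes. Lean body mass appears in the same item, which runs from inclusion to day 10 or discharge, but it has no change wording of its own.

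**The concern.** The baseline value of a repeated measure is usually its strongest single predictor. A model that adjusts handgrip or quality of life for baseline Barthel, a different scale, leaves most of that information unused. Subtracting the baseline recovers part of it. A change score is still less efficient than covariate adjustment whenever the correlation is below 1, and it over-corrects chance imbalance between the arms.

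At stake is the precision of the nutritional, functional and quality-of-life effects. So is a choice that should not stay open in a trial with unblinded patients and caregivers: whether follow-up value, change or baseline-adjusted follow-up is the reported result.

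**Working it through.** **1. The plan's own figure.** The protocol gives no SD, correlation or power for any continuous secondary endpoint, so there is no figure of its own to reproduce on this point. The primary sample size does reproduce. With 0.40 against 0.34, two-sided alpha 0.05 and 90% power, n = [1.960·√(2·0.37·0.63) + 1.282·√(0.24 + 0.2244)]² / 0.06² = 1359 per group, as stated in section 8.3. It does not bear on this point.

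**2. What the text settles.** The opening rule covers every outcome and its list is closed. The Barthel model uses baseline Barthel, centre and NRS, which is the same list. The text therefore cannot show whether Barthel enters as the outcome's own baseline or as a general risk factor, and the opening rule calls it the latter. The sentence on other secondary endpoints names kinds of test and model but no covariates. Own-baseline adjustment is neither stated nor excluded.

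**3. Size: formulas.** Let r be the correlation between baseline and follow-up (assumed), with equal SDs and a large sample. Residual variance relative to the raw follow-up value is:
- own baseline as covariate (ANCOVA): 1 − r²
- change score: 2(1 − r)
- ratio of change to ANCOVA: 2(1 − r)/(1 − r²) = 2/(1 + r)

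If an analysis has 80% power (1.960 + 0.842 = 2.802) and its variance is k times that of ANCOVA, then ANCOVA has power Φ(2.802·√k − 1.960).

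**4. Results.**

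| r (assumed) | ANCOVA / raw | Change / ANCOVA | 80% with change becomes | 80% with raw follow-up becomes |
|---|---|---|---|---|
| 0.5 | 0.75 | 1.33 | 90% | 90% |
| 0.7 | 0.51 | 1.18 | 86% | 97.5% |
| 0.8 | 0.36 | 1.11 | 84% | 99.7% |
| 0.9 | 0.19 | 1.05 | 82% | above 99.9% |

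Example at r = 0.7 against change: √1.176 = 1.085, and Φ(2.802·1.085 − 1.960) = Φ(1.08) = 0.86.

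Seen the other way, where ANCOVA has 80% power, a change score has 68%, 73% and 78% at r = 0.5, 0.7 and 0.9. Raw follow-up has 68%, 52% and 23%.

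**5. With baseline Barthel kept in the model.** Assume baseline Barthel correlates 0.3 with the outcome and 0.4 with the outcome's own baseline. At r = 0.5, 0.7 and 0.9:
- Residual variance with Barthel and own baseline is 0.738, 0.510 and 0.186.
- Change adjusted for Barthel has variance 2(1 − r) − (0.3 − 0.4)² = 0.99, 0.59 and 0.19, giving ratios of 1.34, 1.16 and 1.02.
- Raw follow-up adjusted for Barthel has variance 1 − 0.3² = 0.91, giving ratios of 1.23, 1.79 and 4.90.

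Under these assumptions, adjusting for Barthel barely alters the comparison with change.

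**The case against.** The strongest reply is that section 8.2 is a brief outline and defers detail to an SAP that is not at hand. Outcome-specific covariates commonly belong there, and a list of main risk factors does not bar adding one. The sentence on other secondary endpoints also follows directly on a Barthel model that contains its own baseline, and on a mixed model that includes the admission value. It can fairly be read as own baseline plus centre and NRS. This stands to the extent that nobody can say from the protocol that these endpoints will go unadjusted. It does not remove the literal reading, because the one rule stated for every outcome gives a different, closed list.

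Second, most of these endpoints are worded as improvement or change, so the baseline already enters by subtraction. This stands, and it makes the change score the usual fair comparator. For weight, BMI or grip measured again within about ten days, a high correlation is plausible, which puts the loss at the lower end. A reader might infer the much larger gains in the raw follow-up column. The documents support those only if raw values are analysed. That remains possible for lean body mass, or if the Wilcoxon comparison of day-30 Barthel is copied as the template.

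Third, the consequence is limited. Only secondary endpoints are affected, and under randomisation both approaches are unbiased. With 1000 to 1500 patients per arm and complete data (assumed), an unadjusted comparison already has 80% power for 2.802·√(2/n) = 0.13 to 0.10 SD. This stands as well.

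A reader might also extend the point to section 13.2, which says "Non-parametric bootstrapping will be used to estimate 95%Cls for differences in incremental costs and effects". That text is silent on adjustment, and bootstrapping is compatible with a regression-adjusted difference. It does not state an unadjusted QALY analysis.

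**Conclusion.** The point holds as a matter of wording with a modest cost in precision. The rule in section 8.2 contains the outcome's own baseline only for Barthel, and the text on other secondary endpoints leaves the rest unsettled. Against a change score, the likely comparator, the variance penalty is about 33%, 18% and 5% at assumed correlations of 0.5, 0.7 and 0.9. It is larger only where raw follow-up values are analysed. These sizes rest on equal SDs, a linear model, a large sample and correlations that the protocol does not give. The 80% starting power is illustrative.

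The documents do not support saying that the trial will leave these endpoints unadjusted, that the primary analysis is weakened, or that the Wilcoxon test is wrongly placed. The linear model is already the stated source of effect sizes and intervals, so ranking it above the Wilcoxon test would be a preference.

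**What to change.** Add to section 8.2, and carry into the SAP before database closure, a sentence to this effect: for each continuous secondary endpoint measured at baseline, the adjusted linear model includes that endpoint's own baseline value, study centre and NRS category, together with baseline Barthel's index; missing baseline values are filled by simple imputation so that the patient stays in the model.

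The cost is wording only. The baseline assessments are already planned, and no patients or procedures are added. Under the assumptions above, the adjusted estimate is at least as precise as the alternatives in large samples. The primary analysis, section 13.2 and the role of the Wilcoxon test can stay as they are.
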